## 7.8 Efficacy endpoints

As described in Section 5.1, the FAS will be the basis for the analysis of efficacy data. Only summary tables for Cohorts 2 and 3, non-randomized, and Cohort 2, randomized, (without Cohorts receiving EO2401 column) and none for Cohort 1 are planned (cf. Section 7.1). Further, all summary tables, all Kaplan-Meier (KM) plots, and waterfall plots will be provided by patients fulfilling and not fulfilling extended in/exclusion criteria [REDACTED] for Cohorts 2A, non-randomized.

### 7.8.1 General aspects of response related endpoints

The response assessments during the treatment period follow the scheduled CTs post

baseline, planned for the visits at study weeks 9, 17, 25 (+/- 4 days), and from Week 25 onwards every 8 weeks (+/- 4 days). Unscheduled CT assessments as well as planned CT scans performed on the day of study drug administration [REDACTED]

[REDACTED] are also possible. For patients who are discontinuing all study treatment without having had confirmation of progressive disease (PD) according to iRECIST criteria [Seymour et al], CT assessments are scheduled every 8 weeks (+/- 4 days) after the latest performed CT assessment during the time period they received study treatment.

If not otherwise stated, all response assessments collected by investigator (local assessments) during the study will be considered, regardless of whether they come from scheduled or unscheduled assessments and if they were assessed during or after study treatment.

In principle, any further anti-cancer treatment during the study, i.e. prior to the individual study treatment termination, is prohibited. If nevertheless a patient is treated with further anti-cancer treatment during the study, the inclusion of CT assessments after introduction of further anti-cancer treatment in the derivation of response related and time to event endpoints will be agreed on and documented during the DRM. Also, the non-trial systemic anti-cancer treatments defined in Section 7.8.5 and 7.8.6 will be confirmed during the DRM.

### 7.8.2 Primary endpoint of the phase 2 part: progression-free survival (PFS) rate at 6 months based on investigator / local assessment

[REDACTED] All available data from the monotherapy groups will be reviewed at the same time point.

[REDACTED]

[REDACTED]

[REDACTED]

[REDACTED]

As the first stage of Simon's two-stage design was not conluant, only number and percentage of patients regarded as progression-free survivor at 6 months according to iRECIST and not regarded as progression-free survivor with subcategorical patient died, patient alive, but progressive disease (immune unconfirmed progressive disease [iUPD] or immune confirmed progressive disease [ICPD]), and patient lost to follow-up will be provided in a summary table for Cohort 2A-I, randomized. Further, two-sided 95% exact Clopper-Pearson CIs for binomial proportions will be provided for the progression-free survivor rate at 6 months by cohort.

No further CIs will be provided and no overall analysis for Cohort 2A-II and 2A-III will be performed.

### **7.8.3 Best overall response, objective response, and disease control rate (DCR)**

OR is defined as the best overall response during the whole study period equal to PR or complete response (CR) according to RECIST [Eisenhauer et al] or as best overall response during the whole study period equal to immune partial response (iPR) or immune complete response (iCR) according to iRECIST. No confirmation of PR/CR and iPR/ iCR is required.

The ORR [%] is defined as the relative number of patients achieving OR according to iRECIST/RECIST in the respective cohort. The DCR [%] is defined as the relative number of patients achieving at least one assessment of iCR, iPR, or iSD according to iRECIST in the respective cohort or as the relative number of patients achieving at least one assessment of CR, PR, or SD according to RECIST.

The ORR/DCR according to iRECIST/RECIST will be summarized with two-sided 95% exact Clopper-Pearson CIs for binomial proportions by cohort.

The best overall response according to RECIST will be summarized by cohort, using the following categories and hierarchy: OR (RECIST) with subcategories CR and PR, SD, PD, not evaluable.

The best overall response according to iRECIST will be summarized by cohort using the following categories and hierarchy: OR (iRECIST) with subcategories iCR, iPR, iSD, iUPD, iCPD, not evaluable.

The disease control according to RECIST will be summarized by cohort, using the following categories and hierarchy: disease control (RECIST) with subcategories CR, PR, and SD, and PD, not evaluable.

The disease control according to iRECIST will be summarized by cohort using the following categories and hierarchy: disease control (iRECIST) with subcategories iCR, iPR, and iSD, and iUPD, iCPD, not evaluable.

The maximal shrinkage in tumor burden (i.e. maximal percentage decrease in sum of longest diameter compared to baseline = relative change from baseline) will be displayed

in a waterfall plot. The bars will be colored according to best overall response according to RECIST/iRECIST. Two different colors will be used for PD with new lesion and PD without new lesion. iUPD and iCPD will have the same color. Waterfall plots will be provided for Cohort 2A, Cohort 2B, Cohort 2, non-randomized, for Cohort 3A, Cohort 3B, Cohort 3, and Cohort 2A-I, Cohort 2A-II, and Cohort 2A-III, randomized, and for patients fulfilling and not fulfilling extended in/exclusion criteria (see Section 6.6) of Cohorts 2A, non-randomized.

All response assessments will be listed.

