## 3.2 Study endpoints

### 3.2.1 Primary endpoint

- ***The primary endpoint of the phase 1 part*** includes safety and tolerability of EO2401 in combination with nivolumab by a descriptive medical assessment of the combined profile of incidences of adverse events (AEs), treatment-emergent AEs (TEAEs), serious AEs (SAEs), deaths, reasons for treatment discontinuation/delays, and laboratory abnormalities using the NCI-CTCAE v5.0 grading system [60].
- ***The primary endpoint of the phase 2 part*** is the rate of patients without progression (according to iRECIST criteria [37]) or death due to any cause at 6 months after the first dose of randomized treatment. Six months after the first dose of randomized treatment will be determined for each patient and is dependent on the exact time point of evaluation of the CT investigation scheduled at week 25 (day 169). The primary endpoint is to be determined per investigator/local site assessments of progression. The denominator will be all patients who started the randomized treatment in Cohort 2A\* and will be determined for each randomized treatment group separately. Patients will be followed up for progression or death during the first 6 months after start of randomized treatment regardless of whether they stop treatment and continue on other regimens. Patients who

are completely lost to follow-up will be counted as if they had a PFS event during the first 6 months.

\* Cohort 2A = patients with ACC who had prior systemic therapy for established locally advanced or metastatic disease

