Of special note, unlike RECIST 1.1, the iRECIST criteria requires the confirmation of progression and uses the terms iUPD (unconfirmed progression) and iCPD (confirmed progression). Confirmatory scans should be performed at least 4 weeks, but no longer than 8 weeks after iUPD. Thus, in the current trial, provided that the individual patient is tolerating the administered treatment adequately, it is allowed continuing trial treatment beyond progression as assessed by the RECIST 1.1. criteria for evaluation of progression according to the iRECIST criteria. Provided good tolerability of the trial treatment and lack of new important symptoms indicating clinical tumor progression the confirmatory scans might be obtained at the current trials planned 8 weekly tumor assessment timepoints.

In the context of confirmation of PD per iRECIST, and the timeline of confirmatory scans to be performed at least 4 weeks, but no longer than 8 weeks after iUPD, it should be specifically noted that in case of any signs of rapidly progressing disease establishment of PD and a following therapy switch should be made also earlier than 4-8 weeks after iUPD when necessary.

For all cohorts, and all patients during the whole trial treatment, the following safety rules will apply:

[figure not shown]

Details of the IDMC process and procedures, and Cohort management plan are outlined in a separate Charters.

The schematic trial and cohort designs are presented in [Figure 6](#) and [Figure 7](#).

[figure not shown]
Protocol No: EOADR1-19  
EudraCT: 2019-003396-19

CONFIDENTIAL

Protocol No: EOADR1-19  
EudraCT: 2019-003396-19

CONFIDENTIAL

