### 6.9.3 Prohibited medications and other therapies

The use of systemic corticosteroids and other immunosuppressants should be avoided because of their potential interference with the pharmacodynamics activity of the study treatment. However, in some cases, systemic corticosteroids cannot be avoided; guidance

regarding steroid use for patients participating in the trial is therefore outlined in [Section 6.9.2](#).

The use of live or attenuated vaccine therapy for prevention of infectious diseases during trial participation should be avoided if possible. However, if such vaccinations would be considered as important for the normal care of the patient, the treating physician should discuss the situation with the Medical Monitor of the Sponsor and an adequate solution regarding timing should be found.

Patient should be discouraged from taking medications, including herbal remedies, with immunostimulatory properties, or known to potentially interfere with major organ function, during trial participation. If needed, any such possible therapy should be discussed between the treating physician and the Medical Monitor of the Sponsor.

During trial participation patients should not receive any other anti-cancer treatment than the specific trial treatment (EO2401 in combination with nivolumab) and treatments outlined in [Section 6.9.2](#).

If any other anti-cancer treatment, or procedure, would be considered for start in an individual patient, it is the duty of the Investigator to discuss the consideration with the Medical Monitor of the Sponsor for a decision on how to handle continued trial specific treatment and trial participation.

In general, if necessary due to e.g. patient symptoms, local therapies will be promoted; depending on localization of the treatment versus localization of measurable lesions, a decision might be necessary to consider censoring the patient for progression related endpoints at the time of start of the therapy if there would be no measurable lesion left outside of the location of the local treatment (or assessing the patient as having progressive disease if relevant criteria would be fulfilled).

Start of non-trial systemic anti-cancer treatments would lead to censoring of the patient for progression related endpoints at the time of start of the therapy; or assessment of the patient as having progressive disease if relevant criteria would be fulfilled.

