### 7.5.2 Post-treatment follow-up before assessed progressive disease; Vnn

Patients who are discontinuing all study treatment without having had confirmation of progressive disease according to iRECIST criteria will be followed [REDACTED] after the latest performed CT assessment during the time period they received study treatment.

At these [REDACTED] timepoints the following will be done:

- a CT for tumor status assessment should be performed and tumor response assessment made, as outlined in [Section 7.7](#),

- documentation of safety; after the post-treatment visit for safety assessment (see [Section 7.5.1](#)) has been made, only SAEs with plausible causal relationship with trial treatment will be documented (in addition, in case of death, an as precise cause of death as possible is going to be documented), and
- if applicable, collection of information regarding further anti-cancer treatments.

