##### Target Lesions

When more than one measurable tumor lesion is present at baseline all lesions up to a maximum of 5 lesions total (and a maximum of 2 lesions per organ) representative of all involved organs should be identified as target lesions and will be recorded and measured at baseline. Target lesions should be selected on the basis of their size (lesions with the longest diameter), be representative of all involved organs, but in addition should be those that lend themselves to reproducible repeated measurements. Note that pathological nodes must meet the criterion of a short axis of  $\geq 15$  mm by CT scan and only the short axis of these nodes will contribute to the baseline sum. All other pathological nodes (those with short axis  $\geq 10$  mm but  $< 15$  mm) should be considered non-target lesions. Nodes that have a short axis  $< 10$  mm are considered non-pathological and should not be recorded or followed. At baseline, the sum of the target lesions (longest diameter of tumor lesions plus short axis of lymph nodes: overall maximum of 5) is to be recorded.

After baseline, a value should be provided on the CRF for all identified target lesions for each assessment, even if very small. If extremely small and faint lesions cannot be accurately measured but are deemed to be present, a default value of 5 mm may be used. If lesions are too small to measure and indeed are believed to be absent, a default value of 0 mm may be used.

*Non-target Lesions*

All non-measurable lesions (or sites of disease) plus any measurable lesions over and above those listed as target lesions are considered non-target lesions. Measurements are not required but these lesions should be noted at baseline and should be followed as “present” or “absent”.

*Response*

All patients will have their BEST RESPONSE from the start of study treatment until the end of treatment classified as outlined below:

*Complete Response (CR)*: disappearance of target and non-target lesions and normalization of tumor markers. Pathological lymph nodes must have short axis measures <10 mm (Note: continue to record the measurement even if <10 mm and considered CR). Residual lesions (other than nodes <10 mm) thought to be non-malignant should be further investigated (by cytology, specialized imaging, or other techniques as appropriate for individual cases) before CR can be accepted. Confirmation of response is only required in non-randomized studies.

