#### Confirming Progression

Unlike RECIST 1.1, iRECIST requires the confirmation of progression and uses the terms iUPD (unconfirmed progression) and iCPD (confirmed progression). Confirmatory scans should be performed at least 4 weeks, but no longer than 8 weeks after iUPD.

In the context of confirmation of PD per iRECIST, and the timeline of confirmatory scans to be performed at least 4 weeks, but no longer than 8 weeks after iUPD, it should be specifically noted that in case of any signs of rapidly progressing disease establishment of PD and a following therapy switch should be made also earlier than 4-8 weeks after iUPD when necessary.

iCPD is confirmed if further increase in tumor burden, compared to the last assessment, is seen as evidenced by one or more of the following:

- Continued increase in tumor burden (from iUPD) where RECIST 1.1 definitions of progression had been met (from nadir) in target, non-target disease or new lesions
  - Progression in target disease worsens with an increase of at least 5 mm in the absolute value of the sum
  - Continued unequivocal progression in non-target disease with an increase in tumor burden
  - Increase in size of previously identified new lesion (s) (an increase of at least 5 mm in the absolute value of the sum of those considered to be target new lesions) or additional new lesions.
- RECIST 1.1 criteria are met in lesions types (target or non-target or new lesions) where progression was not previously identified, including the appearance of additional new lesions.

[figure not shown]
If iUPD is not confirmed at the next assessment, then the appropriate response will be assigned (iUPD if the criteria are still met, but no worsening, or iSD, iPR or iCR if those criteria are met compared to baseline). As can be seen in [Table 8](#) and [Table 9](#), the prior documentation of iUPD does not preclude assigning iCR, iPR, or iSD in subsequent time-point assessments or as best overall response (BOR) providing that iCPD is not documented at the next assessment after iUPD.

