**Table 8 : Time-point iRESPONSE**

Target Lesions*	Non-Target Lesions*	New Lesions*	Time Point Response	
			No prior iUPD**	Prior iUPD***, ***
iCR	iCR	No	iCR	iCR
iCR	Non-iCR/Non-iUPD	No	iPR	iPR
iPR	Non-iCR/Non-iUPD	No	iPR	iPR
iSD	Non-iCR/Non-iUPD	No	iSD	iSD
iUPD with no change OR decrease from last TP	iUPD with no change OR decrease from last TP	Yes	NA	NLs confirms iCPD if NLs were previously identified and increase in size ( $\geq 5$ mm in SOM for NLT or any increase for NLNT) or number. If no change in NLs (size or number) from last TP, remains iUPD
iSD	iUPD	No	iUPD	Remains iUPD unless iCPD confirmed based in further increase in size of NT disease (need not meet RECIST 1.1 criteria for unequivocal PD)
iUPD	Non-iCR/Non-iUPD	No	iUPD	Remains iUPD unless iCPD confirmed based on: 
 
○ further increase in SOM of at least 5 mm, otherwise remains iUPD
 

iUPD	iUPD	No	iUPD	Remains iUPD unless iCPD confirmed based on further increase in: 
 
○ previously identified T lesion iUPD SOM <math>\geq 5</math> mm and / or
 
○ NT lesion iUPD (prior assessment - need not be unequivocal PD)
 

iUPD	iUPD	Yes	iUPD	Remains iUPD unless iCPD confirmed based on further increase in: 
 
○ previously identified T lesion iUPD <math>\geq 5</math> mm and / or
 
○ previously identified NT lesion iUPD (need not be unequivocal) and / or
 
○ size or number of new lesions previously identified
 

Non-iUPD/PD	Non-iUPD/PD	Yes	iUPD	Remains iUPD unless iCPD confirmed based on 
 
○ increase in size or number of new lesions previously identified
 

\* Using RECIST 1.1 principles. If no PSPD occurs, RECIST 1.1 and iRECIST categories for CR, PR and SD would be the same. \*\* in any lesion category. \*\*\* previously identified in assessment immediately prior to this TP.

All patients will have their iBOR from the start of study treatment until the end of treatment classified as outlined below.

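### The visible SAP text sets no cut-off for tumor response at the start of post-treatment systemic therapy, so a response after a switch would count for the trial treatment; RECIST DOR also needs an ordering rule

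*SAP*

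**What the plan says.** **Response window.** SAP 7.8.3: "OR is defined as the best overall response during the whole study period" (PR or better, under RECIST 1.1 or iRECIST). No confirmation is required, and one qualifying assessment is enough for disease control. SAP 7.8.1 takes all investigator assessments, scheduled or not, during treatment or after it. Protocol Appendix 1 (12.1) is narrower. For RECIST: "All patients will have their BEST RESPONSE from the start of study treatment until the end of treatment classified as outlined below". For iRECIST: "All patients will have their iBOR from the start of study treatment until the end of treatment classified as outlined below".

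**Other therapy.** SAP 7.8.1 regards further anti-cancer therapy before the end of study treatment as prohibited in principle. If it is given anyway, the data review meeting decides whether later scans count. The same section has that meeting confirm which treatments are non-trial systemic therapy. SAP 7.8.6 defines these as concomitant or post-study medication entered as chemotherapy in the eCRF, mitotane excepted, and makes their start a PFS event.

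**Scans after treatment.** Under protocol 7.5.2 and SAP 7.8.1, patients who stop without confirmed iRECIST progression keep having CTs with response assessment. Protocol 7.5.2 also asks for "if applicable, collection of information regarding further anti-cancer treatments".

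**Duration of response.** SAP 7.8.5 runs RECIST DOR from the first CR or PR to the first documented PD, with details by reference to 7.8.6, where RECIST progression is the first post-baseline CT showing PD. Protocol 4.2 says "it is allowed continuing trial treatment beyond progression as assessed by the RECIST 1.1. criteria", so that progression can be judged by iRECIST.

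**The concern.** Some patients stop study treatment without confirmed progression, start another systemic therapy and are still scanned. If the tumor then shrinks or stabilizes, the SAP as written credits this to the trial treatment, while the same patient has already had a PFS event at the switch. SAP 7.8.4 does not prevent it: only patients without a response are censored at the PFS event, so a response after the switch is an event for time-to-OR.

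The effect has one direction. Adding scans to a best-response derivation can raise ORR and DCR or leave them alone, but cannot lower them. The trial is open-label with local assessment and unconfirmed responses, and the cohorts are small, so one patient is visible in the tables.

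A second gap lies in the RECIST DOR definition. If a PR is recorded after a first PD, nothing in SAP 7.8.5 or 7.8.6 says that the PD ending the response must come after it began.

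**Working it through.** The documents give no figure on this point, so there is none to reproduce.

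**1. Which rule reaches which scan**

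| Scan taken | Visible rule for response |
|---|---|
| On study treatment, no other therapy | counts (SAP 7.8.1) |
| After other therapy begun before study treatment ended | case by case at data review (SAP 7.8.1) |
| After study treatment, no other therapy | counts (SAP 7.8.1) |
| After systemic therapy begun once study treatment ended | none excludes it, so it counts |

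In the last row the therapy is identified at data review, and its start is a PFS event if entered as chemotherapy. Neither step removes the scan.

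**2. Illustration (assumed patients).** Week 25 is day 169 (protocol 3.2.1), so day = 7 × (week - 1) + 1: week 9 = day 57, week 17 = day 113.
- Patient A has SD at week 17, stops treatment, and starts non-trial chemotherapy before the next CT at 113 + 56 = day 169, which shows PR. PFS ends at the chemotherapy start, before day 169. The patient is still a responder, with time-to-OR of 169 days.
- Patient B has unconfirmed progression at week 9, switches, and has SD at week 17. One SD assessment suffices, so disease control changes from no to yes.

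**3. Weight of one patient.** Treated numbers are from SAP 4.2, taken as denominators; points = 100/n.

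| Group | n | Points per patient |
|---|---|---|
| 2A non-randomized | 26 | 3.8 |
| 2B | 7 | 14.3 |
| Cohort 2 (26 + 7) | 33 | 3.0 |
| 3A | 13 | 7.7 |
| 3B | 5 | 20.0 |
| Cohort 3 (13 + 5) | 18 | 5.6 |
| Cohorts 2 + 3 (33 + 18) | 51 | 2.0 |
| 2A-I randomized | 13 | 7.7 |

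For scale, going from 0 to 1 responder moves the upper limit of the exact (Clopper-Pearson) 95% interval from 24.7% to 36.0% (n=13), from 13.2% to 19.6% (n=26) and from 7.0% to 10.4% (n=51).

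**4. RECIST DOR read literally.** SAP 6.5: interval = end - start + 1. With PD at week 9 and PR at week 17, the start is day 113 and the end is day 57, so DOR = 57 - 113 + 1 = **-55 days**.

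**5. iRECIST.** Appendix 1 lets a response follow unconfirmed progression, "providing that iCPD is not documented at the next assessment after iUPD"; its Table 9 sets iBOR to iCPD once progression is confirmed. SAP 7.8.6 does not count an unconfirmed progression that is followed by iSD, iPR or iCR. The DOR problem and response after confirmed progression are therefore largely closed under iRECIST. A switch before confirmation, as in patient B, is not.

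**The case against.** **The data review meeting covers it.** SAP 7.8.1 has non-trial systemic therapies confirmed there, and the 7.8.6 definition includes post-study medication. Under SAP 5.2 the minutes are signed before database lock, and responses and post-treatment medication are listed. This stands as an aid to audit. It does not say what happens to the later scans, and the summary tables would still include them.

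**A rule may be hidden.** SAP 5.3 and parts of 7.8 are redacted. This stands: the point concerns the visible text only.

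**The window conflict is mostly wording.** A reader might infer from Appendix 1 that off-treatment responses are inadmissible. The documents do not support that. Appendix 1 is largely general criteria text, protocol 7.5.2 orders response assessment after treatment, and the ORR endpoint in protocol 3.2.2 carries no end-of-treatment limit. The wordings should be aligned, but the SAP's use of off-treatment scans is defensible.

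**Protocol 3.2.1 does not bear on response.** Its follow-up "regardless of whether they stop treatment and continue on other regimens" concerns progression or death for the 6-month primary endpoint. It should not be read as a plan to score response after a switch.

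**Negative DOR needs a literal reading and a rare course.** The ordinary sense of from response until PD is a PD that comes later. For target-lesion PD at the first scan, the sum must go from at least 120% of baseline to at most 70%, a fall of about 42% (1 - 70/120) in 8 weeks, and a persisting new lesion keeps the time point at PD. Both remarks are fair, so this is a clarification.

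**Should RECIST response simply stop at the first PD?** That is tempting, but neither document says so, and the Appendix 1 window can run past RECIST PD while treatment continues. It is a choice to report, not an error to correct.

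**Conclusion.** The point holds in limited form. As far as the visible text goes, response endpoints have no cut at systemic therapy begun after study treatment, although the SAP already treats that therapy as a PFS event. Any resulting error favors the trial treatment. Per affected patient it is worth 2.0 points (Cohorts 2 + 3) to 20.0 points (3B) of ORR or DCR, taking the SAP 4.2 treated numbers as denominators.

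How many patients are affected is unknown and may be zero. The percentages show sensitivity, and a reader should not infer that the reported ORR is inflated. ORR is one of the other secondary endpoints, behind the key immunogenicity endpoints. The phase 2 primary endpoint does not use best response and is unaffected. The DOR ordering and the Appendix 1 window are secondary points of wording. The conclusion assumes that no cut is stated in the redacted text. It is worth fixing because the change is small and removes a one-directional bias.

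**What to change.** In SAP 7.8.1 and 7.8.3:
- For BOR/iBOR, ORR, DCR, waterfall plots and time-to-OR, exclude assessments after the start of non-trial systemic anti-cancer therapy, whether it begins on or after study treatment. Off-treatment scans before that date still count.
- Use one therapy definition for response and PFS, keeping the SAP's mitotane exception. Reconcile the eCRF chemotherapy wording in SAP 7.8.6 with protocol 6.9.3, which speaks of systemic anti-cancer treatment generally. Reconcile the consequence too: the SAP counts an event, whereas the protocol censors unless progression criteria are met.
- For local therapy, keep the protocol 6.9.3 approach, under which "a decision might be necessary to consider censoring the patient for progression related endpoints at the time of start of the therapy" if no measurable lesion remains outside the treated area, and document each decision at data review.

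In SAP 7.8.5, end DOR at the first PD or death after the response, and state that the start of non-trial therapy is handled in DOR as it is in PFS.

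Report the whole-study version as a sensitivity analysis, and show RECIST responses first seen after RECIST PD separately. Note in the SAP, as a clarification, how its window relates to Appendix 1; this needs no protocol amendment.

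Cost: SAP wording, one date cut in programming and one sensitivity table. ORR and DCR may come out slightly lower.
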